- Failure by the participant to attend multiple clinic visits.
NOTE: This criterion is not applicable when study visits are being conducted remotely, as described in section 8.1.

Letter of Amendment #2

IGHID 11802 - Combination Therapy with the Novel Clearance Modality (VRC07-523LS) and the Latency Reversal Agent (Vorinostat) to Reduce the Frequency of Latent, Resting CD4+ T Cell Infection (The VOR-07 Study), A Phase 1 Study

Protocol Version 4.0, dated 09 May 2019

Letter of Amendment (LoA) #1 Date: August 12, 2019

Clarification Memo #1 Date: September 17, 2019

DAIDS-ES Document Number: DAIDS-ES ID 38536

IND Number: IND 138852

Letter of Amendment (LoA) #2 Date: January 30, 2020

This Letter of Amendment affects the IGHID 11802 study, including the study main informed consent form. Submission to the UNC Institutional Review Board (IRB) overseeing this research will occur as soon as possible after DAIDS review and approval. The UNC IRB must approve this Letter of Amendment before implementation.

Upon receiving final IRB and any other applicable Regulatory Entity (RE) approval(s) for this LoA, UNC will implement per unit SOP. UNC's Regulatory Department retains a copy of this LoA and any associated DAIDS and IRB correspondence in the study's regulatory file. Any future full amendment of the IGHID 11802 protocol will incorporate this Letter of Amendment.

Summary of the Revisions and Rationale

The protocol team is implementing this amendment for the following reasons:

1. To clarify that the acetylation assay and VOR PK samples at the Day 29 and Day 89 visits are collected after taking the 10th Vorinostat dose.
 2. To clarify that a POCT urine test is done on Day 0 and Day 60. Serum pregnancy test will only be done at screening.
 3. To clarify that the Product Lot # will not be on the IP label due to limited space. The lot number is written on the VRC07 523-LS chain of custody form and in the IDS pharmacy logs.
 4. To clarify the dispensing of Vorinostat to participants, providing increased reinforcement of dosing regimen of every 3rd day.
-

Implementation

In changes listed below, additions to current protocol will appear as **bolded text** while deletions to current protocols will appear as ~~crossed-out text~~.

Protocol Changes

1. Clarification to the collection of research labs after 10th dose of Vorinostat in each series.
 - a) Section 1.3, Schedule of Events, page 12

Please note that the grey cells in the isolated segment of the Schedule of Events table below indicate no change. Deleted text appears as ~~crossed-out text~~ and any added text appears as **bolded text** within the table.

	Step 1	Step 2		Step 3		Step 4
	All Visit	All Visits	Day 29	All visits	Day 89	All visits
Research Lab Procedures						
All other samples						
Single PK sample (VOR) ⁴			X		X	
Acetylation, Virology and Viral Sequence Analysis			X ⁴		X ⁴	

⁴ Draw samples approximately 4 hours post dose (+/- 1 hour)

- b) Research Laboratory Assays, page 58
This modification is added to correct a typographical error. There are only 2 VOR PK samples collected on the study, but erroneously listed as 3 in this text.

Vorinostat PK samples

Pharmacokinetic samples will be collected at **2** ~~3~~-time points in the study **per SOE**. These will be processed and stored for testing as required.

- c) Research Laboratory Assays, page 58
Acetylation, Virology and Viral Sequence Analysis
Samples will be collected per the SOE. Samples will be processed, stored, and analyzed as required.

2. Clarification of Pregnancy Testing
 - a) Section 1.3, Schedule of Events, page 11.

Please note that the grey cells in the isolated segment of the Schedule of Events table below indicate no change. Deleted text appears as ~~crossed-out text~~ and any added text appears as **bolded text** within the table.

	Step 1	Step 2		Step 3		Step 4
	Screen	Day 0	All other visits	Day 60	All other visits	All visits
Clinical Lab Procedures						
All other samples						
Serum Pregnancy Test	X	✗	X ³	✗	X ³	X ³
Urine Pregnancy Test (POCT)		X		X		

³ Serum pregnancy test will be performed at any time **during the study**, if pregnancy suspected. ~~serum pregnancy test must be completed on day of intervention to confirm pregnancy status~~

b) Section 8.2 Safety and other Assessments

Clinical Laboratory Testing for Safety, page 61

Serum and Urine Pregnancy Test, 2nd paragraph

A negative ~~serum~~ **urine** pregnancy test (**POCT**) is required ~~at each visit~~ prior to **each** VRC07-523LS infusion, and within 72 hours of the first VOR dose in Step 2 and Step 3 regardless of documented procedures that prohibit pregnancy.

3. Clarification of Investigational Product Lot # on IV bag

a) Section 6.2.4 Preparation, page 48

VRC07-523LS, Section 3, Intravenous Infusion Preparation Instructions

g) Label the IV bag with:
(last bullet)

- ~~lot number~~

4. Clarification of Vorinostat Dispensing

a) Section 6.1.2 Dosing and Administration

Vorinostat, page 43

The study provides the Vorinostat 400 mg to the participants. In Step 2 and Step 3, participants will take their first dose of VOR 400 mg PO at home two (2) days after the VRC07-523LS infusion. ~~All participants will be dispensed 5 doses of VOR 400 mg at the infusion visits on Day 0 and Day 60.~~ All participants will be provided with instructions for the safe administration of VOR at home. **VOR will be dispensed at the following study visits:**

Day 0 – 2 doses

Day 7 – 3 doses

Day 14 – 5 doses

Day 60 – 5 doses

Day 74 – 5 doses

Participants will return to the CTRC on ~~the day of their 5th dose (Day 14 and Day 74)~~ for safety labs and evaluations. ~~and to receive their last 5 doses of VOR 400 mg.~~

Informed Consent Changes

1. Page 6 - Day 0, Visit 3
 - 2nd bullet point - If female, we will do a pregnancy ~~urine blood~~ test.
 - 8th bullet point - Give you ~~5~~ **2** doses of VOR 400 mg to take home with you.

2. Page 6 – Day 7, Visit 4
 - 1st bullet point – Come to clinic. **Bring your empty medication bottle, Post-infusion and VOR Dosing Logs.**
 - 6th bullet - Review and discuss your VOR dosing **log.**
 - Add 7th bullet – Give you the next 3 doses of VOR and a new VOR dosing log.**
 - Add 8th bullet – Review the VOR dosing schedule with you and provide you with a dosing log that will list the days you need to take your doses.**

3. Page 7, Day 29, Visit 6
 - 1st bullet – Come to clinic **approximately 4 hours after taking you 10th (last) dose of VOR. Discuss with your study coordinator, the time you will take your last dose of VOR and the time you should be at your clinic visit.**

4. Page 7, Day 60, Visit 8
 - 2nd bullet point - If female, we will do a pregnancy ~~urine blood~~ test.

5. Page 8, Day 89, Visit 11
 - 1st bullet – Come to clinic **approximately 4 hours after taking you 10th (last) dose of VOR. Discuss with your study coordinator, the time you will take your last dose of VOR and the time you should be at your clinic visit.**

Letter of Amendment #2

IGHID 11802 - Combination Therapy with the Novel Clearance Modality (VRC07-523LS) and the Latency Reversal Agent (Vorinostat) to Reduce the Frequency of Latent, Resting CD4+ T Cell Infection (The VOR-07 Study), A Phase 1 Study

Protocol Version 4.0, dated 09 May 2019

Letter of Amendment (LoA) #1 Date: August 12, 2019

Clarification Memo #1 Date: September 17, 2019

DAIDS-ES Document Number: DAIDS-ES ID 38536

- ~~3. Use of any agent that suppresses lymphocytes or monocyte function;~~
4. Use of chemotherapeutic agents, growth factors, cytokines, or chemokines, white lineage colony stimulating factors (e.g., granulocyte-colony stimulating factor [G-CSF] and GM-CSF);
5. Chronic use of topical corticosteroids that are applied to large areas of the skin (exceeding the cumulative area of the palm of the participant's hand) ~~or any corticosteroids or antihistamines used on or near the infusion site.~~
6. Standard and live vaccinations (e.g., varicella, measles, mumps, rubella, MMR; yellow fever, oral polio) are permitted but timing of vaccine must be discussed and approved by the study PI or designee.
7. ~~Antihistamine can be administered only if needed to treat an anaphylactic reaction.~~

Letter of Amendment #1

IGHID 11802 - Combination Therapy with the Novel Clearance Modality (VRC07-523LS) and the Latency Reversal Agent (Vorinostat) to Reduce the Frequency of Latent, Resting CD4+ T Cell Infection (The VOR-07 Study), A Phase 1 Study

Protocol Version 4.0, dated 09 May 2019

DAIDS-ES Document Number: DAIDS-ES ID 38536

IND Number: IND 138852

Letter of Amendment (LoA) #1 Date: August 12, 2019

This Letter of Amendment affects the IGHID 11802 study, including the study main informed consent form. Submission to the UNC Institutional Review Board (IRB) overseeing this research will occur as soon as possible after DAIDS review and approval. The UNC IRB must approve this Letter of Amendment before implementation.

Upon receiving final IRB and any other applicable Regulatory Entity (RE) approval(s) for this LoA, UNC will implement per unit SOP. UNC's Regulatory Department retains a copy of this LoA and any associated DAIDS and IRB correspondence in the study's regulatory file. Any future full amendment of the IGHID 11802 protocol will incorporate this Letter of Amendment.

Summary of the Revisions and Rationale

The protocol team is implementing this amendment for the following reasons:

- To relax some of the inclusion and exclusion criteria currently limiting enrollment.
- Suggested changes do not increase the risk to participants.
- To correct the blood volume for Visit 3 (Day 0) in the estimated blood volume table.

Implementation

In changes listed below, additions to current protocol will appear as **bolded text** while deletions to current protocols will appear as ~~crossed out text~~.

Protocol Changes

1. Section 5.1 Inclusion Criteria (pages 35 - 38)
Note changes to selected criteria below:

#4 - On continuous antiretroviral therapy (ART defined in 5.1.5) for at least 24 months prior to screening.

Note: Continuous ART prior to screening is defined as not missing more than ~~4(four)~~ 9 total days ~~and never more than 2 consecutive days~~ in the 3 months prior to screening.

2. Section 5.2 Exclusion Criteria (pages 38 – 41)

Note changes to selected criteria below:

#12 - Prior **receipt of** ~~use of any~~ HIV immunotherapy within ~~6~~ 12 months prior to screening.

~~#13 – Prior use of an HIV vaccine prior to screening.~~

#15 - Prior receipt of humanized or human mAbs **within 2 months prior to screening**, whether licensed or investigational, will have eligibility determined by the study PI on a case-by-case basis.

#27 - Diabetes Mellitus type 1 ~~or type 2~~

~~Not exclusionary: type 2 cases controlled with diet alone or a history of isolated gestational diabetes~~

NOTE: Individuals with type 2 diabetes who meet inclusion criteria for glucose (Section 5.1.23) are not excluded.

#29 - Hypertension - Exclude for blood pressure consistently >150 mm Hg systolic and >100 mm Hg diastolic.

- ~~• If a person has been found to have elevated blood pressure or hypertension during screening or previously, exclude for blood pressure that is not well controlled. Well-controlled blood pressure is defined as consistently \leq 140 mm Hg systolic and \leq 90 mm Hg diastolic, with or without medication, with only isolated, brief instances of higher readings, which must be \leq 150 mm Hg systolic and \leq 100 mm Hg diastolic. For these volunteers, blood pressure must be \leq 140 mm Hg systolic and \leq 90 mm Hg diastolic at enrollment.~~
- ~~• If a person has NOT been found to have elevated blood pressure or hypertension during screening or previously, exclude for systolic blood pressure \geq 150 mm Hg at enrollment or diastolic blood pressure \geq 100 mm Hg at enrollment.~~

Note: Elevated BP occurring during research leukapheresis procedures completed within the past 12 months are excluded from this requirement. ~~Other isolated incidences of~~

~~elevated BP should be reviewed by study PI (or designee) to determine whether they are exclusionary.~~ Acceptable isolated elevations must be noted as acceptable and signed by study PI or designee.

3. Estimated Blood Volumes Associated with the Study Visits (page 64)

Visit or Week #	Blood Volume (mL)	Visit or Week #	Blood Volume (mL)
Visit 1	50	Visit 8 Day 60	116

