16. Received any infusion blood product, immune globulin, or hematopoietic growth factors within 90 days prior to study entry.
17. Pregnancy or breast-feeding.
18. History or other evidence of severe illness, malignancy, immunodeficiency other than HIV, or any other condition that would make the participant unsuitable for the study in the opinion of the investigator, for at least 90 days prior to screening.
19. History of autoimmune disease

Not exclusionary: Persons with mild, stable, and uncomplicated autoimmune disease that do not require immunosuppressive medication and that, in the judgement of the site investigator (or designee), is likely not subject to exacerbation and likely not to complicate AE assessments.

20. Use of topical steroids over a total area exceeding 15 cm² within 30 days prior to Screening.
21. Treatment for an active AIDS-defining opportunistic infection within 90 days prior to Screening.

22. History of malignancy within the last 5 years.

NOTE: A history of non-melanoma skin cancer (e.g., basal cell carcinoma or squamous cell skin cancer) is not exclusionary with documentation of complete resection at least 3 months prior to enrollment).

23. Compulsorily detained (involuntarily incarcerated) for treatment of either a psychiatric illness or a physical illness, e.g., infectious disease.

24. Known psychiatric, medical, occupational, or substance abuse disorders that would interfere with participant's ability to fully cooperate with the requirements of the trial as assessed by the study investigator (or designee).

Specifically exclusionary: [1] recent psychosis; [2] ongoing risk for suicide; or [3] recent history of suicide attempt or gesture.

25. History or other clinical evidence of a significant medical condition that includes but is not limited to:

- a) A process that would affect the immune response
- b) A process that would require medication that affects the immune response
- c) Any contraindication to repeated injections, infusions, or blood draws
- d) A condition or process (e.g., chronic urticarial or recent injection or infusion with evidence of residual inflammation) for which signs and symptoms could be confused with reactions to the study product

26. Current anti-tuberculosis therapy

27. Diabetes Mellitus type 1 or type 2

Not exclusionary: type 2 cases controlled with diet alone or a history of isolated gestational diabetes

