28. History of coronary artery disease, congestive heart failure, or cardiac arrhythmia requiring current treatment prior to study screening.

29. Hypertension

- If a person has been found to have elevated blood pressure or hypertension during screening or previously, exclude for blood pressure that is not well controlled. Well-controlled blood pressure is defined as consistently ≤ 140 mm Hg systolic and ≤ 90 mm Hg diastolic, with or without medication, with only isolated, brief instances of higher readings, which must be ≤ 150 mm Hg systolic and ≤ 100 mm Hg diastolic. For these volunteers, blood pressure must be ≤ 140 mm Hg systolic and ≤ 90 mm Hg diastolic at enrollment.
- If a person has NOT been found to have elevated blood pressure or hypertension during screening or previously, exclude for systolic blood pressure ≥ 150 mm Hg at enrollment or diastolic blood pressure ≥ 100 mm Hg at enrollment.

Note: Elevated BP occurring during research leukapheresis procedures completed within the past 12 months are excluded from this requirement. Other isolated incidences of

elevated BP should be reviewed by study PI (or designee) to determine whether they are exclusionary. Acceptable isolated elevations must be noted as acceptable and signed by study PI or designee.

30. Unstable asthma (e.g., sudden acute attacks occurring without an obvious trigger) or either of the following in the past 12 months:
 - a) >1 exacerbation of symptoms treated with oral/parenteral corticosteroids;
 - b) Emergency care, urgent care, hospitalization, or intubation for asthma.
31. Bleeding disorder diagnosed by a doctor (e.g., factor deficiency, coagulopathy, or platelet disorder requiring special precautions).
32. Seizure disorder: History of seizure(s) within past three years or use of medications used to prevent or treat seizure(s) at any time within the past 3 years.
33. History of asplenia – absence of normal spleen function as indicated by:
 - a) Splenectomy
 - b) Sickle cell disease
34. History of hereditary angioedema, acquired angioedema, or idiopathic angioedema.
35. Prisoner recruitment and participation is not permitted.

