- Poor adherence to ART as judged by the site Principal Investigator or designee.
- Request by the participant to withdraw from the study and study procedures.
- Request of the participant's primary care provider if she/he thinks the study is no longer in the best interest of the participant.
- Participant judged by the study Principal Investigator to be at significant risk of failing to comply with the provisions of the protocol, as to cause harm to self or seriously interfere with the validity of the study results.
- At the discretion of the IRB/Ethics Committee, FDA, NIH, and other government agencies as part of their duties, Principal Investigator, or industry supporter.

Premature Treatment Discontinuation Evaluations

Participants who begin but do not complete all doses of VRC07-523LS and VOR will be replaced. The collection of virologic, immunologic, and 2nd leukapheresis samples following premature discontinuation will be determined on a case-by-case basis in discussion with the protocol team.

Participants who complete Steps 2 and 3 but are unable to complete the leukapheresis (#2) in Step 4 will contribute to safety analyses and complete an end of study visit. The ability to complete virologic and immunologic endpoint analysis will be determined on a case-by-case basis in discussion with the protocol team. Replacement will be determined by the protocol team based on the ability to complete endpoint analysis.

Delaying VRC07-523LS administration

Under certain circumstances, a participant's scheduled VRC07-523LS infusion may be delayed. The factors to be considered in such a decision include but are not limited to the following:

Within 7 days prior to any study product administration

- Receipt of systemic glucocorticoids (e.g., prednisone or other glucocorticoids) or other immunomodulators (other than nonsteroidal anti-inflammatory drugs [NSAIDs]) – *Please reference paragraph below as these medications are prohibited on study.*
- Pre-infusion abnormal vital signs or clinical symptoms that may mask assessment of study product reaction.
- Inability to dose with VOR due to clinical symptom or laboratory value.
- Intercurrent illness that is not expected to resolve prior to the VRC07-523LS infusion which is assessed by the site principal investigator (or designee) to require delay or withdrawal from the study product administration schedule.

Infusions should not be administered outside the visit window periods.

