8.3.4 TIME PERIOD AND FREQUENCY FOR EVENT ASSESSMENT AND FOLLOW-UP

The occurrence of an adverse event (AE) or serious adverse event (SAE) may come to the attention of study personnel during study visits and interviews of a study participant presenting for medical care, or upon review of medical record.

The study unsolicited AE reporting period will be from enrollment (Day 0) through the end of study visit. During Step 1 (period between consent and Day 0), any AE that occurs will be collected as concurrent medical history (pre-existing condition) and not as an AE, unless it is due to a protocol-related procedure (leukapheresis).

All AEs including local and systemic reactions not meeting the criteria for SAEs will be captured in the research record on the appropriate form. Information collected includes:

- Event description,
- Time of onset,
- Study PI's (or designee's) assessment of severity, relationship to study product and expectedness,
- Time of resolution/stabilization of the event.

All AEs occurring while on study must be documented appropriately regardless of relationship. All AEs will be followed to adequate resolution.

Any medical condition that is present at the time that the participant is screened will be considered baseline and not reported as an AE. However, if the study participant's condition deteriorates at any time during the study, it will be recorded as an AE.

Changes in the severity of an AE will be documented to allow an assessment of the duration of the event at each level of severity to be performed. AEs characterized as intermittent require documentation of onset and duration of each episode.

The study research coordinator will record all reportable events with start dates occurring any time on or after the enrollment visit until 7 (for non-serious AEs) or 30 days (for SAEs) after the last day of study participation. At each study visit, the research coordinator will inquire about the occurrence of AE/SAEs since the last visit. Events will be followed for outcome information until resolution or stabilization.

Clinical Laboratory Changes:

Safety laboratory assessments will be carried out locally at UNC and evaluated by the Investigator (or designee) to ensure participant safety. The Investigator (or designee) is responsible for reviewing the results of all laboratory tests as they become available.

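### Amended exclusion #29 joins the systolic and diastolic limits with *and*, so sustained elevation on one measure alone no longer excludes

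*Combined protocol and SAP*

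**What the plan says.** Section 5.2, exclusion #29, in protocol Version 4.0 (09 May 2019) has two bullets.

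- **Elevated pressure found at screening or earlier.** Exclude if not well controlled. "Well-controlled blood pressure is defined as consistently ≤ 140 mm Hg systolic and ≤ 90 mm Hg diastolic", with a small allowance for isolated, brief higher readings.
- **No elevated pressure found.** The instruction is to "exclude for systolic blood pressure ≥ 150 mm Hg at enrollment or diastolic blood pressure ≥ 100 mm Hg at enrollment".

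Letter of Amendment #1 (August 12, 2019) strikes both bullets and substitutes one sentence: "Exclude for blood pressure consistently >150 mm Hg systolic and >100 mm Hg diastolic". It keeps the note that sets aside readings taken during research leukapheresis and the requirement that acceptable isolated elevations be signed off. It deletes the sentence sending other isolated elevations to the study PI for review.

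The letter's summary gives relaxation of criteria that limit enrollment as a reason for the changes. It adds: "Suggested changes do not increase the risk to participants".

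**The concern.** The conjunction does opposite work in the two texts. In the first Version 4.0 bullet, *and* defines acceptable pressure: both readings must be within limits, so failing either one excludes. In the amended sentence, *and* sits inside the exclusion itself, so both limits must be exceeded before anyone is excluded. It looks as though the word was carried over when the sentence was turned round, although the documents do not say so.

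The consequence is that #29 no longer acts on isolated systolic or isolated diastolic hypertension, however severe. A sustained 200/95 would pass it.

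The limit matters in this setting for three reasons:

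- Section 2.3.1 lists hypertension among possible infusion reactions and blood pressure fluctuation among the common effects of leukapheresis.
- Section 8.1 (Leukapheresis) says pressure rises during that procedure will not be used to end participation, so the entry limit carries more of the protection.
- Section 2.3.2 states that participants receive no direct medical benefit.

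**Working it through.** The plan states no figure to reproduce here. The check is a comparison of four rules applied to sustained readings, with systolic S and diastolic D in mm Hg.

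**Rules**

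- Version 4.0, bullet 1 (Section 5.2 #29, elevation known): exclude unless S ≤ 140 and D ≤ 90.
- Version 4.0, bullet 2 (Section 5.2 #29, none known): exclude if S ≥ 150 or D ≥ 100 at enrollment.
- Amended rule (Letter of Amendment #1): exclude if S > 150 and D > 100.
- Proposed rule: exclude if S > 150 or D > 100.

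**Excluded by #29?**

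| Reading | V4.0 bullet 1 | V4.0 bullet 2 | Amended (*and*) | Proposed (*or*) |
|---|---|---|---|---|
| 170/85 | yes | yes | **no** | yes |
| 140/110 | yes | yes | **no** | yes |
| 160/105 | yes | yes | yes | yes |
| 145/95 | yes | no | no | no |
| 150/100 | yes | yes | no | no |

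For 170/85, S exceeds 150 but D does not exceed 100, so the amended condition fails. For 140/110, D exceeds 100 but S does not exceed 150, with the same result. The two Version 4.0 bullets cover different people, so only one column applies to any individual. Both columns exclude these two readings, so the comparison does not depend on which bullet applied.

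The last two rows show what *or* preserves. The amended rule is more permissive than Version 4.0 in three ways: higher limits than bullet 1, strict inequalities where bullet 2 had *at or above*, and the both-measures condition. Using *or* removes only the third.

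**Does other text close the gap?**

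- Exclusion #18 reaches "any other condition that would make the participant unsuitable for the study in the opinion of the investigator". This is discretionary and has no blood pressure value.
- Exclusion #25 covers "History or other clinical evidence of a significant medical condition that includes but is not limited to" a list of items that sets no blood pressure value.
- Section 7.2 allows an infusion to be delayed for "Pre-infusion abnormal vital signs or clinical symptoms that may mask assessment of study product reaction". This too has no value, and it comes too late for the baseline leukapheresis at Visit 2, which precedes Day 0.
- The retained note to #29 concerns isolated elevations and readings during leukapheresis, not sustained elevation.
- Letter of Amendment #2 (January 30, 2020) does not touch #29.

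**Effect on the primary endpoint.** None is claimed. Under Section 8.3.4, "Any medical condition that is present at the time that the participant is screened will be considered baseline and not reported as an AE", unless the condition deteriorates.

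**The case against.** The strongest reply is that the letter set out to relax eligibility, and requiring both limits is one way to do that. Nothing in the documents says the *and* was unintended. That stands: a drafting slip is an inference. However, the letter does not say that marked elevation on one measure was meant to become acceptable, and such a change fits poorly with its statement on risk.

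A second reply is that clinicians may read the sentence as a list of two separate limits, one per measure. That reading is possible. If it is the intended one, *or* says it plainly and changes nothing; if staff apply the sentence literally, *or* closes a real gap.

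Third, a single-site team takes vital signs at every clinic visit and repeatedly around each infusion, and exclusion #28 removes coronary disease, heart failure and treated arrhythmia. A sustained 170/85 would be noticed, and the team could act on it. This reduces the practical risk but does not supply a threshold.

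Fourth, Clarification Memo #1 (September 17, 2019) post-dates the letter, and its text is not visible here, so a later correction cannot be ruled out. The letter's markup is also imperfect: for #12 it shows a change to 12 months, which Version 4.0 already states. That oddity does not explain a wholly new sentence under #29.

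Finally, few people would be affected. That is correct, and it limits the weight of the point.

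**Conclusion.** The concern holds. Read literally, amended #29 excludes only when both limits are exceeded, and sustained single-measure hypertension that Version 4.0 excluded is left to investigator judgement. This should be corrected as a participant-safety wording matter; it bears on no sample size, power or endpoint calculation.

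The size in people cannot be stated. The documents give no prevalence, and at most 12 participants are planned.

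The conclusion rests on the literal reading of the conjunction and on there being no later correction of #29 outside the visible text.

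**What to change.** In exclusion #29, replace *and* with *or*, so that a consistent systolic pressure above 150 mm Hg or a consistent diastolic pressure above 100 mm Hg excludes. Keep the relaxed limits and the retained note as they are.

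This is one word, and can go through a clarification memo or the next letter of amendment. The cost is that a few candidates with sustained elevation on one measure would be turned away; Version 4.0 would have excluded them too. If the team did intend both limits to be required, the letter should say so and explain why that is consistent with no increase in risk.
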